## **10.2 Auditing and Inspecting**

The investigator will permit study-related monitoring, audits, and inspections by the IRB/EC, the sponsor, government regulatory bodies, and University compliance and quality assurance groups of all study related documents (e.g. source documents, regulatory documents, data collection instruments, study data etc.). The investigator will ensure the capability for inspections of applicable study-related facilities (e.g. pharmacy, diagnostic laboratory, etc.).

Participation as an investigator in this study implies acceptance of potential inspection by government regulatory authorities and applicable University compliance and quality assurance offices.

## **11 Ethical Considerations**

This study is to be conducted accordance with applicable US government regulations and international standards of Good Clinical Practice (GCP), and applicable institutional research policies and procedures.

This protocol and any amendments will be submitted to a properly constituted Institutional Review Board (IRB) in agreement with local legal prescriptions, for formal approval of the study conduct. The decision of the IRB concerning the conduct of the study will be made in writing to the investigator and a copy of this decision will be provided to the sponsor before commencement of this study. The investigator should provide a list of IRB members and their affiliate to the sponsor.

All subjects for this study will be provided a consent form describing this study and providing sufficient information for subjects to make an informed decision about their participation in this study. This consent form will be submitted with the protocol for review and approval by the IRB for the study. The formal

CONFIDENTIAL

This material is the property of the NYU School of Medicine and Langone Medical Center. Do not disclose or use except as authorized in writing by the study sponsor

consent of a subject, using the IRB-approved consent form, must be obtained before that subject undergoes any study procedure. The consent form must be signed by the subject or legally acceptable surrogate, and the investigator-designated research professional obtaining the consent.

## 12 Study Finances

### 12.1 Funding Source

Funding for conducting the trial will be provided by EMD Serono/Merck KGaA. The investigational agent (Avelumab) will be provided to patients enrolled on this study by EMD Serono/Merck KGaA.

### 12.2 Conflict of Interest

Any investigator who has a conflict of interest with this study (patent ownership, royalties, or financial gain greater than the minimum allowable by their institution, etc.) must have the conflict reviewed by a properly constituted Conflict of Interest Committee with a Committee-sanctioned conflict management plan that has been reviewed and approved by the study sponsor prior to participation in this study. All NYULMC investigators will follow the applicable University conflict of interest policies.

### 12.3 Subject Stipends or Payments

No patient or subject will receive payments or stipends for participation in this research study. EMD Serono/Merck KGaA may provide coverage for tests and/or procedures that are a part of the research study, if it is not covered by the subject's insurance.

## 13 Publication Plan

NYULMC fulfills its commitment to publicly disclose the results of studies.

The overall Principal Investigator, [name]., Ph.D., holds the primary responsibility for publication of the study results. The co-investigators of this study must first obtain approval from [name], the primary responsible party for publication, before any information collected in this trial can be used or passed on to a third party. Neither the complete nor any part of the results of the study carried out under this protocol, nor any of the information provided by the overall Principal Investigator for the purposes of performing the study, will be published or passed on to any third party without the consent of the study overall Principal Investigator. Any investigator involved with this study is obligated to provide the overall Principal Investigator with complete test results and all data derived from the study.

EMD Serono/Merck KGaA has no objection to publication by the study overall Principal Investigator of any information collected or generated by the study overall Principal Investigator, whether or not the results are favorable to the investigational drug. However, to ensure against inadvertent disclosure of confidential information or unprotected inventions, Investigator will provide EMD Serono/Merck KGaA an opportunity to review any proposed publication or other type of disclosure before it is submitted or otherwise disclosed.

## 15 Attachments

**Attachment 1: Schedule of Events**

**Attachment 2: Karnofsky Performance Status Scale**

**Attachment 3: iRANO Criteria**

**Attachment 4: Recommended Dose Modification or Discontinuation and Supportive Care Guidelines for Specific Drug-Related Adverse Events**

**Attachment 5: Factors to Consider in Assessing the Relationship of AEs to Avelumab or Infusion Procedure, Study Procedure, or Combination Treatment**

**Attachment 6: Technical Specifications and Structural Considerations for Planning Radiotherapy**

**Attachment 7: Research Correlative/Biomarker Studies: Background and Rationale**

CONFIDENTIAL

This material is the property of the NYU School of Medicine and Langone Medical Center. Do not disclose or use except as authorized in writing by the study sponsor

## 15.1 Attachment 1: Schedule of Events

STUDY DAY ►	Day -21 to -1 	C1 D1 	C1 D8 	C1 D15 	C2 D1	C2 D15	D1 of C3+	End of Rx 	30-Day Post-Drug 	90-Day Post-Drug 
Study Team Procedures										
Informed Consent 	X									
Demographics	X									
Inclusion/Exclusion Criteria 	X									
Medical/Disease History 	X									
KPS Assessment 	X	X			X		X	X	X	
Concomitant Medications 	X	X			X		X	X	X	
Height and Weight 	X	X		X	X	X	X	X	X	
Vital Signs 	X	X	X	X	X	X	X	X	X	
Complete Physical Exam 	X	X			X		X	X		
Directed Physical Exam 			X	X		X			X	
Adverse Events 		X	X		X		X	X	X	X
Survival								X	X	X
Laboratory/Cardiology Assessments										
Serum Chemistry 	X	X		X	X	X	X	X	X	
Hematology 	X	X		X	X	X	X	X	X	
Urinalysis 	X			X	X	X	X	X		
Coagulation 	X									
Hepatitis B and C 	X									
Pregnancy Test 	X	X			X		X	X		
TSH, free T4 	X	X					X (every other cycle)	X 		
12-Lead ECG	X									
Study Treatment										
Radiotherapy: 5 Gy x 5 fractions (25 Gy total) 			X 							
Avelumab IV 		X		X	X	X	X			
Imaging Assessments										
MRI Brain Scan 	X						X			
Chest X-ray 	X									
Research Samples										
Archival tumor tissue 	X									
Research blood samples 		X			X					
Tumor biopsy (optional) 								X		

### EXPLANATION OF SUPERSCRIPTS:

1. Screening will start within 21 days prior to initiation of study treatment (first dose of Avelumab).
2. Informed Consent: Performed by MD attending only. Informed consent process to be fully documented: e.g. prospective participant had sufficient time for deliberation, all questions were answered, treatment options provided by MD, full study reviewed including risks, and a copy of signed consent given to the participant. No study specific screening procedures may occur until after the informed consent process is complete. Informed consent may be obtained more than 21 days before the start of screening procedures. Assessments performed as part of standard of care that fall within the screening window but before informed consent is obtained may be used for screening, and need not be repeated for enrollment eligibility.

### CONFIDENTIAL

This material is the property of the NYU School of Medicine and Langone Medical Center. Do not disclose or use except as authorized in writing by the study sponsor

3. Inclusion/exclusion criteria: source documentation providing investigator's confirmation that the participant had met all eligibility criteria must be available prior to registration.
4. C1D1 assessments must be performed within 3 days prior to the first dose of Avelumab.
5. If well tolerated and no tumor progression, clinic visits and laboratories will be conducted every 2 weeks with radiographic assessment performed every 8 weeks (approximately every 2 cycles). For all study visits subsequent to C1D8, required assessments must be performed within 3 days of each scheduled Visit Day.
6. All patients must have histopathological documentation of a prior lower-grade (WHO grade II or III) glioma on a previous biopsy specimen and documentation of temozolomide or PCV chemotherapy prior to transformation to glioblastoma (WHO grade IV). All patients must have histopathological diagnosis of glioblastoma, WHO grade IV, at progression from the prior grade II or III glioma. The diagnosis of glioblastoma must be confirmed by central review prior to registration. An *IDH1* or *IDH2* mutation must be present in at least one tumor specimen. Subjects who received anti-tumor therapy after histopathologic transformation to glioblastoma must have shown unequivocal radiographic evidence of tumor progression by contrast-enhanced MRI scan (or CT scan if MRI is contraindicated). Medical history should also include review of all treatment history for GBM and any ongoing medical conditions and medical history pertaining to eligibility on study and involvement during study.
7. After registration, all patients will be required to provide a tumor block with a minimum of 1 cm^2 of tumor surface area from a previous tissue specimen that demonstrates pathological transformation to glioblastoma (WHO grade IV). If a tumor block cannot be submitted, then 20 unstained slides (preferably 10 slides from two different tumor blocks from the same surgery) from the tumor specimen must be submitted.
8. Karnofsky Performance Status (KPS) assessment: See **Attachment 2** for KPS scale.
9. Concomitant medication recording will be ongoing throughout the course of the study. Record concomitant medications from within 21 days before starting study treatment up to the 30-Day Post Drug Visit.
10. Height is required only at screening. Weight can be taken within 3 days of scheduled study drug administration.
11. Vital signs include temperature, resting blood pressure, pulse, and respiration rate. When scheduled at the same visit as other procedures, vital signs should be measured prior to clinical laboratory assessments or research blood sample collection. At C1D1, vital signs will be collected prior to treatment, at the end of the infusion, and 30 minutes post-infusion. Vital signs on subsequent treatment days of cycle 1 and all subsequent cycles will be assessed and documented prior to the infusion and then approximately 30 minutes after the completion of the infusion (all infusion VS timepoints  $\pm$ 10 minutes). Following all Avelumab infusions, subjects must be observed for 30 minutes post-infusion for potential infusion-related reactions. During Radiation Therapy, vital signs will only be recorded on the first day of radiation therapy (C1D8).
12. Complete physical exam to be completed by the investigator or qualified designee at screening, C1D1 and start of all subsequent cycles. Complete physical exam includes skin, head, eyes, throat, neck, joints, lungs, heart, abdomen (including liver and spleen), lymph nodes, extremities, and neurological exam. The exam may be performed within 3 days prior to the day of each scheduled study visit.
13. Symptom-directed physical exam to be completed as clinically indicated by the investigator or qualified designee on the first day of radiation therapy (C1D8) and at all mid-cycle visits (i.e. Day 15).
14. Serum Chemistry includes: sodium, potassium, chloride, bicarbonate, calcium, magnesium, phosphorous, glucose, albumin, creatinine, blood urea nitrogen (BUN), uric acid, ALT, AST, total bilirubin, direct and/or indirect bilirubin, alkaline phosphatase (ALP), and lactate dehydrogenase (LDH). Samples may be collected within 3 days prior to the scheduled day of each visit.
15. Hematology includes: WBC count, 3-cell differential (ANC, monocyte count, lymphocyte count), hemoglobin, hematocrit, and platelet count. Samples may be collected within 3 days prior to each scheduled study visit.
16. Urinalysis: glucose, blood, pH, specific gravity, ketones, and urine protein. Samples may be collected within 3 days prior to each scheduled study visit.
17. Coagulation – PT/INR, PT, PTT required at screening only.
18. Urine or serum  $\beta$ -HCG for women of child-bearing potential at screening and at Day 1 of every cycle.
19. TSH (thyroid stimulating hormone) and free T4 (free thyroxine) at C1D1, every other cycle thereafter, and at end of treatment or 30 days post-treatment safety follow-up (if not performed in the previous 8 weeks).
20. Hypofractionated radiation therapy (HFRT): Administered 5 Gy per fraction for 5 fractions over 5 consecutive days. Total HFRT dose will be 25 Gy. See **Attachment 6** for technical details of HFRT. On the first day (C1D8) of HFRT, adverse event assessment, a symptom-directed physical exam and limited vital signs (temperature, resting blood pressure, pulse, and respiration rate) must be performed.
21. Study drug (Avelumab) administration windows include  $\pm$ 3 days of scheduled visit. Avelumab will be administered in an outpatient setting as an IV infusion. Each patient's dose will depend on individual body

CONFIDENTIAL

- weight. The dose of Avelumab must be adjusted each dose for changes in body weight of  $\geq 10\%$ . Dose adjustments for changes in body weight of  $< 10\%$  will be at the discretion of the investigator.
22. Contrast-enhanced brain MRI for response assessment will be performed prior to C1D1, then prior to C3D1, and then every 8 weeks thereafter. Initial imaging should be performed within 14 days prior to first dose of study treatment (Avelumab). MRIs can be performed within 7 days (-7 days) of scheduled assessment. On-study imaging should follow calendar days (every 8 weeks) and should not be adjusted for delays in cycle starts. A contrast-enhanced CT can be performed if MRI is contraindicated. Local reading (investigator assessment) will be used to determine eligibility and for participant management. Response Assessments will be performed on every brain imaging assessment performed on protocol per iRANO criteria (see **Attachment 3**).
  23. Research Blood Samples: For all patients, whole blood will be drawn at two timepoints: C1D1 (pre-dose) and at C2D1. For subjects at NYULMC, four purple top EDTA tubes (40 mL) will be drawn, one EDTA tube will be sent to the CBRD and three EDTA tubes will be sent immediately to the IMC. For subjects at other sites: **\*Subsites should NOT schedule research blood draws on Fridays as the NYU CBRD will not be able to receive specimens on weekends.** 40 mL of blood will be drawn into two types of tubes: 10 mL will be drawn into one Cell-Free DNA BCT® collection tube and 30 mL will be drawn into three purple top EDTA (10 mL) tubes. Blood samples will be immediately shipped overnight to NYULMC per instructions in the **Lab Manual**.
  24. Optional tumor biopsy: If subjects undergo tumor resections or biopsies during the study period after treatment initiation, or after progression on HFRT + Avelumab, a tumor specimen will be collected for research purposes. For details see **Section 6.8.3** and **Attachment 7**.
  25. Monitored throughout the study via safety assessments, observation, and participant reporting.
  26. End of treatment assessments to be performed within 7 days after the last drug administration or within 7 days after decision to end treatment. After the end of treatment, each subject will be followed for 30 days for adverse event monitoring and 90 days for serious adverse event reporting. Assessments may continue for ongoing reportable adverse events. After coming off study, patients will be contacted every 3 months to assess survival status.
  27. A site visit is to be performed at 30 days ( $\pm 7$  days) after the last study drug is given, unless the subject is unable to travel due to deteriorating medical condition, due to the potential risk for delayed immune-related toxicities. All participants will be followed until resolution or stabilization of any serious or reportable adverse events occurring during treatment or starting within 30 days of last study drug.
  28. Given the potential risk for delayed immune-related toxicities, safety follow-up must be performed up to 90 days ( $\pm 14$  days) after the last dose of avelumab administration. The extended safety follow-up beyond 30 days after last study drug administration may be performed either via a site visit or via a telephone call with subsequent site visit requested in case any concerns noted during the telephone call. This may be performed via documented phone conversation with a study nurse or physician.
  29. Hepatitis B virus surface antibody, hepatitis B virus surface antigen, hepatitis B virus core antibody, and hepatitis C virus antibody at screening only.
  30. Chest x-ray is required at screening if not performed within 60 days prior to initiation of study treatment.

CONFIDENTIAL

**15.2 Attachment: 2**

***Karnofsky Performance Status Scale***

Karnofsky Performance Scale	
Percent	Description
100	Normal, no complaints, no evidence of disease.
90	Able to carry on normal activity; minor signs or symptoms of disease.
80	Normal activity with effort; some signs or symptoms of disease.
70	Cares for self, unable to carry on normal activity or to do active work.
60	Requires occasional assistance, but is able to care for most of his/her needs.
50	Requires considerable assistance and frequent medical care.
40	Disabled, requires special care and assistance.
30	Severely disabled, hospitalization indicated. Death not imminent.
20	Very sick, hospitalization indicated. Death not imminent.
10	Moribund, fatal processes progressing rapidly.
0	Dead.

CONFIDENTIAL

This material is the property of the NYU School of Medicine and Langone Medical Center. Do not disclose or use except as authorized in writing by the study sponsor

### 15.3 Attachment: 3

## ***iRANO (immunotherapy response assessment in neuro-oncology) Criteria***

Tumor response will be assessed every 8 weeks for patients treated on this study using modified iRANO criteria as outlined in the **Study Procedures (Section 6)**.

### **Anti-Tumor Effect Definitions**

Evaluable for objective response. Only those participants who have measurable disease present at baseline (obtained within 14 days of cycle 1, day 1) scan and have received at least one dose of therapy will be considered evaluable for response. These participants will have their response classified according to the definitions stated below. (Note: Participants who exhibit objective disease progression or die prior to the end of cycle 1 will also be considered evaluable.)

Measurable disease. Bi-dimensionally, contrast-enhancing, measurable lesions with clearly defined margins by CT or MRI scan, with a minimal diameter of 1 cm, and visible on 2 axial slices which are at least 5 mm apart with 0 mm skip. Measurement of tumor around a cyst or surgical cavity, if necessary, requires a minimum thickness of 3 mm. If there are too many measurable lesions to measure at each evaluation, the investigator must choose the largest two to be followed before a participant is entered on study. The remaining lesions will be considered non-measurable for the purpose of objective response determination. Unless progression is observed, objective response can only be determined when all measurable and non-measurable lesions are assessed.

Non-measurable evaluable disease. Unidimensionally measurable lesions, masses with margins not clearly defined, lesions with maximal diameter < 1cm.

### **Response/Progression Categories**

Complete response (CR). All of the following criteria must be met:

1. Complete disappearance of all enhancing measurable and non-measurable disease sustained for at least 4 weeks. In the absence of a confirming scan 4 weeks later, this scan will be considered only stable disease.
2. No new lesions\*.
3. All measurable and non-measurable lesions must be assessed using the same techniques as baseline.
4. Participants must be on no steroids or must not be on increased doses of steroids within 2 weeks of assessment relative to the dose taken at the time of the previous assessment
5. Stable or improved non-enhancing (T2/FLAIR) lesions
6. Stable or improved clinically, for clinical signs and symptoms present at baseline and recorded to be disease related

*Participants with non-measurable disease cannot have a complete response. The best response possible is stable disease.*

*\*See immunotherapy considerations below regarding new lesions*

Partial response (PR). All of the following criteria must be met:

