##### **5.5.2 Acceptable Concomitant Medications**

All treatments that the investigator considers necessary for a subject's welfare may be administered at the discretion of the investigator in keeping with the community standards of medical care.

Physiologic replacement doses of systemic corticosteroids are permitted after consultation with the overall PI or designee, even if >10 mg/day prednisone equivalents. Standard doses of hydrocortisone for maintenance therapy are 10–20 mg/m^2/day divided 2–4 times per day. For a subject with a body surface area (BSA) of 1.73 m^2, this translates to a total dose of 34.6 mg of

CONFIDENTIAL

hydrocortisone per day. The equivalent dose of dexamethasone is 1.2 mg per day. Some subjects may additionally receive mineralocorticoid-replacement maintenance therapy with fludrocortisone. The maintenance dose of fludrocortisone for this indication is 0.05–0.1 mg/day.

Intranasal, inhaled or topical corticosteroids (<5% of body surface area) for the treatment of mild/moderate asthma, allergies or dermatitis are permitted. Antihistamines and other non-steroidal anti-allergy medications are also permitted. A brief course of corticosteroids for prophylaxis (e.g., contrast dye allergy) or for treatment of non-autoimmune conditions (e.g., delayed-type hypersensitivity reaction caused by contact allergen) is permitted.

During the study, bevacizumab is permitted and preferred over corticosteroids for management of symptoms related to intracranial/brain edema or central nervous system radiation necrosis. See **Rules for Brain Edema** in **Section 5.2.1.2** for guidelines on management of symptoms related to intracranial/brain edema, bevacizumab administration, and corticosteroid use in this setting.

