#### CONFIDENTIAL

1. Greater than or equal to 50% decrease compared to baseline in the sum of products of perpendicular diameters of all measurable enhancing lesions sustained for at least 4 weeks. In the absence of a confirming scan 4 weeks later, this scan will be considered only stable disease.
2. No progression of non-measurable disease.
3. No new lesions.\*
4. All measurable and non-measurable lesions must be assessed using the same techniques as baseline.
5. Participants must be on no steroids or must not be on increased doses of steroids within 2 weeks of assessment relative to the dose taken at the time of the previous assessment
6. Stable or improved non-enhancing (T2/FLAIR) lesions on same or lower dose of corticosteroids compared to baseline scan.
7. Stable or improved, for clinical signs and symptoms present at baseline and recorded to be disease related clinically.

*Participants with non-measurable disease cannot have a partial response. The best response possible is stable disease.*

*\*See immunotherapy considerations below regarding new lesions*

Progressive disease (PD). Any of the following criterion must be met:

1. 25% increase in sum of the products of perpendicular diameters of enhancing lesions (over best response or baseline if no decrease) on stable or increasing doses of corticosteroids
2. Patients who decrease corticosteroid use within 2 weeks of MRI assessment relative to the dose taken at the time of the previous assessment cannot be classified as having progressive disease and should be classified as non-evaluable.
3. Any new enhancing measurable lesion\*
4. Clear clinical deterioration not attributable to other causes apart from the tumor (e.g. seizures, medication side effects, complications of therapy, cerebrovascular events, infection, etc.). The definition of clinical deterioration is left to the discretion of the investigator but it is recommended that a decline in the Karnofsky Performance Score (KPS) from 100 or 90 to 70 or less, a decline in KPS of at least 20 from 80 or less, or a decline in KPS from any baseline to 50 or less, for at least 7 days, be considered neurologic deterioration, unless attributable to co-morbid events or changes in corticosteroid dose.
5. Failure to return for evaluation due to death or deteriorating condition

*\*See immunotherapy considerations below regarding new lesions*

Stable disease (SD). All of the following criteria must be met:

1. Does not qualify for CR, PR, or progression.

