### Summary of iRANO Response Criteria

Complete response	Disappearance of all enhancing disease for $\geq 4$ weeks; no new lesions; stable or improved T2/FLAIR; no more than physiological steroids; clinically stable or improved
Partial response	$\geq 50\%$ decrease in the sum of biperpendicular diameters of enhancing disease for $\geq 4$ weeks; no new lesions; stable or improved T2/FLAIR; stable or decreased steroid dose; clinically stable or improved
Minor response	NA
Stable disease	Does not qualify for complete response, partial response, or progressive disease; no new lesions; stable or improved T2/FLAIR; stable or decreased steroid dose; clinically stable or improved
Progressive disease	$\geq 25\%$ decrease in the sum of biperpendicular diameters of enhancing disease; or new lesions; or substantial worsened T2/FLAIR; or substantial clinical decline

[figure not shown]
**Note:** iRANO recommends confirmation of disease progression on follow-up imaging 3 months after initial radiographic progression if there is no new or substantially worsened neurological deficits that are not due to comorbid events or concurrent medication, and it is 6 months or less from starting immunotherapy. If follow-up imaging confirms disease progression, the date of actual progression should be back-dated to the date of initial radiographic progression. The appearance of new lesions 6 months or less from the initiation of immunotherapy alone does not define progressive disease. FLAIR=fluid-attenuated inversion recovery.

**Note:** Typographical error in the Progressive Disease definition, the correct criteria should be "increase" rather than "decrease".

CONFIDENTIAL

This material is the property of the NYU School of Medicine and Langone Medical Center. Do not disclose or use except as authorized in writing by the study sponsor

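### Attachment 3 sets conflicting steroid conditions for complete and partial response, with no statement of which text governs, and its summary table also words the size threshold differently from the list

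*Combined protocol and SAP*

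**What the plan says.** Radiographic response rate and median duration of response are secondary endpoints (Section 3.3), and the response rate is to be reported with an exact 95% interval (Section 7.2.2). Attachment 3 (Section 15.3) defines response twice.

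**Numbered list (Response/Progression Categories)**
- CR item 4: "Participants must be on no steroids or must not be on increased doses of steroids within 2 weeks of assessment relative to the dose" at the previous assessment. CR item 5 asks only for "Stable or improved non-enhancing (T2/FLAIR) lesions", with no steroid condition.
- PR item 5 repeats CR item 4. PR item 6 adds "Stable or improved non-enhancing (T2/FLAIR) lesions on same or lower dose of corticosteroids compared to baseline scan".
- PR item 1 sets the size threshold as at least a 50% "decrease compared to baseline in the sum of products of perpendicular diameters of all measurable enhancing lesions sustained for at least 4 weeks".

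**Table (Summary of iRANO Response Criteria)**
- CR row: "stable or improved T2/FLAIR; no more than physiological steroids; clinically stable or improved".
- PR row: the steroid dose must be stable or decreased. No reference time is given.
- PR row size threshold: at least a 50% "decrease in the sum of biperpendicular diameters of enhancing disease for" four weeks or more. The progressive-disease row uses the same diameter wording at 25%.

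The opening of Attachment 3 says participants are classified by the definitions that follow. The sentence before the table presents it as a summary of the criteria the study will use. Neither is given precedence. The note under the table corrects one slip, in the progressive-disease row, and leaves these differences alone.

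**The concern.** A response hierarchy should make the higher category at least as hard to reach as the lower one. In the list, the steroid conditions run the other way: PR is tied to the baseline dose and CR is not. The table reverses this, with a physiological ceiling for CR and an open-ended condition for PR.

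Steroids can reduce enhancement, which is why these conditions exist. The plan calls brain edema common after fractionated brain radiation and allows corticosteroids for it (Section 5.2.1.2, Rules for Brain Edema; Section 5.5.3). Scans are 8 weeks apart, so a dose started between two scans is the previous-assessment dose one scan later and then satisfies CR item 4.

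The plan describes local investigator reading (Section 6.6) at four sites, and I find no central response read. Two readers following different parts of the same attachment could classify one patient differently. What is at stake is the reported CR rate, in some cases the response rate, and which patients enter the duration-of-response analysis.

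**Working it through.** **The plan's own design figures.** These concern six-month progression-free survival (PFS6) only; no target or power is stated for response. For the two-stage rule (stop at 7 or fewer of 18; success at 23 or more of 43), the probability of success is the sum over x = 8 to 18 of Bin(x; 18, p) × P(X₂ ≥ 23 − x), with X₂ ~ Bin(25, p). At p = 0.40 this is 0.0474 (stated 0.047). At p = 0.60 it is 0.827 (stated 82.7%). Both reproduce, and neither depends on the CR or PR rules.

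**Steroid conditions.** Section 5.5.2 gives a worked physiological replacement dose at a body surface area of 1.73 m²: "The equivalent dose of dexamethasone is 1.2 mg per day". That uses the top of its hydrocortisone range (20 × 1.73 = 34.6 mg); the bottom (10 mg/m²) would give half, 0.6 mg. A dose of 4 mg/day, which exclusion criterion 9 does not bar at entry, is therefore 4/1.2 = 3.3 to 4/0.6 = 6.7 times physiological. The cases below use illustrative dexamethasone doses in mg/day at baseline / previous scan / current scan. Enhancement is gone for at least 4 weeks unless noted, and all other conditions are met.

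| Case | Doses | By the list | By the table |
|---|---|---|---|
| A | 4 / 4 / 4 | CR | PR |
| B | 0 / 4 / 4 | CR | Not CR; PR only if stable means versus the previous scan |
| B, but a 60% decrease in products | 0 / 4 / 4 | Not PR (item 6) | Depends on the same missing reference time, with size read as products |
| C | 0 / 0 / 1 | Neither CR nor PR (dose increased) | CR |

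Case A changes the CR/PR split and leaves CR + PR the same. Case B changes responder status if stable is measured from baseline. Case C changes it in the opposite direction. The two B rows together show that the list's CR rule is looser than its PR rule.

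**Effect on the rate.** One patient is 1/43 = 2.3 percentage points. The 43 is an assumption: Section 7.2.2 refers to all who start therapy, but Section 6.9 and Attachment 3 limit response evaluability to measurable baseline disease, which gives a smaller denominator and a larger step. For illustration, with assumed counts, 8/43 is 18.6% (exact 95% interval 8.4 to 33.4%) and 7/43 is 16.3% (6.8 to 30.7%).

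**Size threshold, read literally, with equal proportional shrinkage in both directions**
- List: a 50% fall in the product means each diameter falls by 1 − √0.5 = 29.3%.
- Table: a 50% fall in the sum of diameters means each diameter falls by 50%, so the product falls by 1 − 0.5² = 75%.
- Example: 3.0 × 2.0 cm shrinking to 2.1 × 1.4 cm. The product goes from 6.0 to 2.94 (−51%); the diameter sum goes from 5.0 to 3.5 (−30%). This is PR by the list and not by the literal table.
- Progressive disease: a 25% rise in the product is √1.25 − 1 = 11.8% per diameter. A 25% rise in diameters is 1.25² − 1 = 56% in the product.

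**The case against.** The strongest reply is that the list defines and the table abbreviates. The list says all its items must be met, it directly follows the statement that participants are classified by the definitions given, and the table is introduced as a summary. That is the natural reading, but it is nowhere stated. It also leaves the CR rule looser than the PR rule, because that asymmetry lies within the list itself.

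The size difference is probably shorthand. Attachment 3 requires bi-dimensional measurement and the list spells out products in full. This largely stands, so I treat the size wording as secondary: it should be corrected because it would change classifications if applied literally.

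A reader might infer several stronger points that the documents do not support:
- That steroid doses allowed at entry inflate the response rate. If the dose is unchanged from baseline (case A), the patient moves only from CR to PR.
- That steroid-assisted responses are to be expected here. Sections 5.2.1.2 and 5.5.2 prefer bevacizumab to corticosteroids for edema, and Section 5.5.3 advises against systemic steroids outside listed exceptions. Steroids are permitted, but no frequency is given for patients like case B.
- That CR has no absolute steroid limit anywhere. That is true of the list only; the table has one.
- That the primary endpoint is compromised. The diameter wording does appear in the progressive-disease row, but the list gives products there too, and the PFS6 design calculations are untouched.

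**Conclusion.** The conflict is real and lies in the current text. On steroids, the list and the table disagree about CR, the list makes CR looser than PR, and the table's PR row has no reference time. For some patients the classification, and sometimes responder status, depends on which text is applied.

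The size is modest: about 2.3 points of response rate per patient whose status changes, assuming 43 in the denominator, and no change in CR + PR when the supraphysiological dose has been constant since baseline. One such shift is small beside the exact interval. How many patients would be affected cannot be estimated from the documents. The endpoints touched are secondary and unpowered, with no decision rule attached. It is still worth correcting before responses are read, so that the rule is not chosen once results are known.

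**What to change.** In Attachment 3:

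1. Keep the no-increase condition in CR item 4 and add the table's physiological limit to it. Replacing the item outright would drop the no-increase condition and turn case C into a CR. Align the table's CR row with the combined condition.
2. State how physiological is to be judged for classification. Section 5.5.2 offers a worked example, not a defined cut-off.
3. State the baseline scan as the reference for the steroid condition in the table's PR row, as in list item 6.
4. Word the size thresholds in the table's PR and progressive-disease rows as sums of products of perpendicular diameters.
5. State that the numbered list governs the response-rate and duration-of-response analyses.

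This prevents CR on a supraphysiological dose. One narrow asymmetry would remain: a physiological dose begun after baseline and then held could pass CR but fail PR item 6. The authors should say whether they intend that.

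The change concerns response classification only, not how steroids are used. The cost is wording: steroid doses and dates are already recorded (Section 5.5.1) and lesion diameters are already measured. The CR rate, and possibly the response rate, may come out slightly lower.
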